7.2.4.2 Secondary endpoints and analysis method

[Secondary endpoints]

1) Progression-free survival (PFS)

PFS is the period from the day of enrollment until the day of documented PD (radiological decision or clinical decision) or the day of death due to any cause, whichever comes earlier.

For surviving subjects without documented progression, the period will be cut off on the final day on which progression-free status is confirmed (final day of progression-free survival confirmation). Events and the cut-off will also be handled the same way in subjects who have discontinued protocol treatment for reasons such as toxicity and refusal of treatment, even if another (follow-up) therapy is added. Thus, the time of treatment discontinuation or the day of follow-up treatment initiation will not be the cut-off.

[Analysis method]

Kaplan-Meier method will be used to illustrate survival curve until the onset of event in the “full analysis set,” and the point estimation value of survival rate and its 95% confidence interval (two-sided) will be calculated at the quartile of PFS and specified time points. The

Log-Log conversion of Brookmeyer and Crowley will be used to calculate the 95% confidence intervals of the quartiles for PFS.

2) Overall survival (OS)

OS is the period from the day of enrollment until death by any cause. For surviving subjects, the period is terminated on the final day of survival confirmation or data cut-off date, whichever occurs earlier.

[Analysis method]

Kaplan-Meier method will be used to illustrate survival curve until the onset of event in the “full analysis set,” and the point estimation value of survival rate and its 95% confidence interval (two-sided) will be calculated at the quartile of OS and specified time points. The Log-Log conversion of Brookmeyer and Crowley will be used to calculate the 95% confidence intervals of the quartiles for OS.

3) Response rate (RR)

RR is the percentage of subjects whose best overall response after enrollment according to RECIST ver. 1.1 is either complete response or partial response. Overall response will be graded by favorability in the order of complete response (CR), partial response (PR), stable disease (SD), progressive disease (PD), and not evaluable (NE). Best overall response is the best response recorded throughout all courses.

[Analysis method]

RR of target lesion and its 95% confidence interval (two-sided) will be calculated in the “full analysis set.”

Further, the maximum tumor reduction rate will be calculated for each subject, and a waterfall plot will be created by arranging the maximum tumor reduction rate in ascending order. Lines of reference at -30% indicating PR and at + 20% indicating PD will be drawn.

$$\text{Reduction ratio of SoD} = \frac{\text{SoD at evaluation point} - \text{SoD before treatment}}{\text{SoD before treatment}} \times 100\%$$

4) Duration of response (DOR)

DOOR is the period from the day when either CR or PR is first confirmed until the day of documented PD or the day of death due to any cause, whichever occurs earlier. For surviving subjects without documented PD, the period will be cut off on the final day of progression-free survival confirmation.

[Analysis method]

The Kaplan-Meier survival curve will show the subject status until the onset of event for the subjects who showed response among the “full analysis set,” and the point estimation value of survival rate and its 95% confidence interval (two-sided) will be calculated at the quartile of DOOR and specified time points.

5) Disease control rate (DCR)

DCR is the percentage of subjects whose best overall response after enrollment according to RECIST ver. 1.1 is CR, PR, or SD.

[Analysis method]

DCR and its 95% confidence interval (two-sided) will be calculated in the “full analysis set.”

6) Time to treatment failure (TTF)

TTF is the period from the day of enrollment until the day of the decision to discontinue protocol treatment, the day of documented progression during protocol treatment (day of decision on clinical PD or radiological PD), or the day of death due to any cause, whichever comes earlier. Subjects not included in the above criteria will be censored at the dose starting date in the final course.

[Analysis method]

Kaplan-Meier method will be used to illustrate survival curve until the onset of event in the “full analysis set,” and the point estimation value of survival rate and its 95% confidence interval (two-sided) will be calculated at the quartile of TTF and specified time points. The Log-Log conversion of Brookmeyer and Crowley will be used to calculate the 95% confidence intervals of the quartiles for TTF.

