9.2.10 Imaging test (thoracoabdominal-pelvic CT/MRI)

Imaging test will be performed within 4 weeks (28 days) prior to enrollment (including the same day of week as the day of enrollment). The results of imaging diagnosis/test performed before obtaining consent may be used if it is performed within 4 weeks (28 days) prior to enrollment.

Furthermore, the data of measurable lesion should be evaluated with imaging test conducted within 2 weeks (14 days) prior to initiation of protocol treatment (including the same day of week as the day of enrollment) preferably. If another imaging test has been conducted newly after enrollment but before initial administration, this data should be recorded in CRF.

After initiation of protocol treatment, imaging test will be performed every 8 weeks (56 days) with protocol treatment initiation date (Day 1) of Course 1 as the starting point. However, when 1 year has passed since initiation of protocol treatment, imaging may be performed once every 12 weeks (84 days), counting from the point in time at which 1 year has passed. (For details, see “Table 9.a Study calendar (phase I part of the study)” or “Table 9.b Study calendar (phase II part of the study).”

Thoracoabdominal-pelvic CT (in principle, contrast CT; a slice width of 5 mm or less is recommended, but MRI is also acceptable) will be used for imaging test, and the modality and the date of imaging test will be entered into the CRF. If necessary, brain MRI / CT and a neck CT will be performed.

In principal, the same modality should be used for imaging test during protocol treatment throughout the study period.

The investigator or the subinvestigator should evaluate the test results according to the RECIST v1.1 (see Appendix A) and enter the determined results into the CRF.

Furthermore, for subjects withdrawn from the study for any reason other than imaging test results such as clinical PD, imaging test specified at the time of discontinuation should be performed within 4 weeks (28 days) including the day of decision (including the same day of week as the day of decision).

If the subject is not determined to have PD on imaging up to the time of withdrawal, the following information should be collected until the subject dies or the sponsor terminates the study, even after follow-up treatment has been started.

- Day of decision on clinical PD (only when the subject is not determined to have clinical PD by the time of discontinuation)

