13.3.3.2 Secondary endpoints and analysis method

[Secondary endpoints]

- Progression-free survival (PFS)

PFS is the period from the day of enrollment until the day of documented progression or the day of death due to all causes whichever comes earlier.

Progression will include both PD based on diagnostic imaging assessed according to RECIST ver 1.1 (see Appendix A) and primary disease progression that cannot be confirmed by diagnostic imaging (clinical progression). When progression is documented by diagnostic imaging, the day that the diagnostic imaging is performed will be the progression date. For clinical progression, the day of the clinical determination will be the progression date. In a case where, for example, tumor diameter has become extremely small, if the status is determined to be “not definite progression” clinically, although the assessment is PD according to the response criteria, the assessment of PD according to the response criteria will take precedence and the status will be considered progression. (In this case, the clinical determination on continuing protocol treatment will take precedence.) Even if the assessment is not PD according to the response criteria, if there is definite clinically documented progression, the clinical determination will take precedence and the status will be considered progression. For surviving subjects without documented progression, the period will be cut off on the final day when a progression-free status is confirmed (final day of confirming progression-free survival). Confirmation of progression-free status by imaging test or sample test is not mandatory, and clinical confirmation by outpatient medical examination, etc., will be allowed. Contact by

CONFIDENTIAL

telephone only will not be allowed.) Events and the cut-off will also be handled the same way in subjects who have discontinued protocol treatment for reasons such as toxicity and refusal of treatment, even if another (follow-up) therapy is added. Thus, the time of treatment discontinuation or the day of follow-up treatment initiation will not be the cut-off.

[Analysis method]

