organ can be recorded as 1 lesion (e.g. multiple enlarged pelvic lymph nodes, multiple liver metastases)

4. Tumor response criteria

Evaluate target lesion and non-target lesion using the same method as at enrollment according to “9.2.10 Imaging test (thoracoabdominal-pelvic CT/MRI)“, and record diameter of target lesion, presence or absence of non-target lesion or onset of new lesion.

5. Response criteria of target lesion

• CR (Complete Response):

Disappearance of all non-nodal target lesions and all lymph node target lesions short axis <10mm If nodal target lesion is selected at baseline, response criteria may be CR even though SoD is not 0 mm.

• PR (Partial Response):

At least a 30% decrease in the SoD of target lesions, taking as reference the baseline SoD.

• PD (Progressive Disease):

Taking as reference the smallest sum on study (this includes the baseline sum if that is the smallest on study), at least a 20% increase in the SoD of target lesions, and the sum must also demonstrate an absolute increase of at least 5 mm.

• SD (Stable Disease):

Neither sufficient shrinkage to qualify for PR nor sufficient increase to qualify for PD, taking as reference the smallest SoD while on study.

• Not all Evaluated:

When test cannot be conducted for some reason, or cannot be determined as CR, PR, PD or SD.

$$\text{Reduction ratio of SoD} = \frac{\text{SoD before treatment} - \text{SoD at evaluation}}{\text{SoD before treatment}} \times 100\%$$

$$\text{Increase ratio of SoD} = \frac{\text{SoD at evaluation} - \text{Smallest SoD}}{\text{Smallest SoD}} \times 100\%$$

* Diameter of target lesion is recorded with actual measurements (e.g., even if under 5 mm) as much as possible, but when target lesion is determined as “too small to measure”, irrespective of CT slice thickness, if it is determined that tumor lesion no longer exists and the diameter will be recorded as 0 mm, whereas if it is determined to exist the diameter will be 5 mm.

- * If reduction ratio meets the PR criteria and increase ratio meets the PD criteria at the same time, criteria will be determined as PD.
- * If one lesion is divided during treatment, each diameter should be added to the SoD.
- * If multiple lesions agglutinate and the border cannot be distinguished, the diameter of the agglutinated lesion should be added to the SoD.
- * Whenever lesions are in contact, if the borders of the lesions are distinguishable, the diameter of each lesion should be added to the SoD.

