reported as a “new” cystic lesion, which it is not. A newly identified lesion in a location by test that was not mandatory at baseline (evaluation before enrollment) is considered a new lesion. If a lesion disappears and reappears later, measurement will be continued. However, the response at the time of reappearance of the lesion will be different depending on other lesions. If lesion has reappeared after CR, it will be determined as PD at the time of reappearance. On the other hand, if it was PR or SD, when the once disappeared lesion reappears, in order to calculate the response, the diameter of the lesion will be added to the rest of the lesions. Thus, when there are a number of lesions still existing, if one lesion apparently “disappears” and reappears later, from that alone, it will not be determined as PD but if the SoD of all the lesions meet the PD criteria, it will be determined as PD. The reason for this is that there is an understanding that most of the lesions do not truly “disappear” and yet it cannot be extracted due to the limit to resolution of imaging modality.

If there is a possibility of new lesion but cannot be confirmed, it should not be determined as a new lesion but re-examination by imaging test should be conducted after clinically appropriate interval. If new lesion is confirmed by imaging test re-examination, the date of the imaging test that confirmed the new lesion will be the time point for appearance of new lesion.

8. Overall Response

Overall Response will be determined with combination of target lesion response, non-target lesion response, appearance of new lesion according to Tables A.1 and A.2 below.

Table A.1 Overall response at each time point: When patient has target lesion (with or without non-target lesion)

Target lesion	Non-target lesion	New lesion	Overall response
CR	CR	Absent	CR
CR	Non-CR/non-PD	Absent	PR
CR	Not determined	Absent	PR
PR	Non-PD or defect in evaluation	Absent	PR
SD	Non-PD or defect in evaluation	Absent	SD
Defect in evaluation	Non-PD	Absent	NE
PD	Any	Present or absent	PD
Any	PD	Present or absent	PD
Any	Any	Yes	PD

9. Best Overall Response

Response will be more favorable in the following order: CR>PR>SD>PD>NE. The most favorable overall response through the entire course will be the best overall response.

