When response could not be determined by imaging due to an obvious aggression of disease or death before the first response determination, it will be determined as PD. When response could not be determined by imaging due to discontinuation from toxicity or rejection by subject before the first response determination, it will be determined as NE.

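### Best overall response sets no minimum time for SD and does not end at progression, so a subject who stops before the first scheduled scan with an unchanged discontinuation scan counts as disease control

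*SAP*

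**What the plan says.** SAP v4.0 section 7.2.4.2, item 3, ranks overall response in the order CR, PR, SD, PD, NE and adds: "Best overall response is the best response recorded throughout all courses". Item 5 builds on this: "DCR is the percentage of subjects whose best overall response after enrollment according to RECIST ver. 1.1 is CR, PR, or SD". Protocol Appendix A, item 9, has the same rule: "The most favorable overall response through the entire course will be the best overall response".

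Appendix A, item 5, defines SD by size alone: "Neither sufficient shrinkage to qualify for PR nor sufficient increase to qualify for PD, taking as reference the smallest SoD while on study". It gives no interval from baseline or from the start of treatment.

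Item 9 has two defaults for subjects without a first response determination. The first begins "When response could not be determined by imaging due to an obvious aggression of disease or death before the first response determination" and assigns PD. The second covers stopping for toxicity or refusal and assigns NE. Both are conditional on imaging not having given a response.

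Protocol section 9.2.10 schedules scans every 56 days from Day 1 of Course 1, and Table 9.c allows ± 7 days in the first year. For subjects who stop for a reason other than imaging, clinical PD being the named example, the "imaging test specified at the time of discontinuation should be performed within 4 weeks (28 days) including the day of decision".

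For PFS, Protocol section 13.3.3.2 and SAP section 7.2.4.1 let clinical judgement override the scan: "Even if the assessment is not PD according to the response criteria, if there is definite clinically documented progression, the clinical determination will take precedence". Neither text extends this to best overall response, and Table A.1 in Appendix A has no entry for clinical progression.

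**The concern.** Disease control should mean that the disease was held at least until the first planned look at it. As written, one unchanged scan at any time after enrolment is enough, and the protocol itself asks for such a scan from subjects who stop early. A short interval makes an unchanged scan more likely, whatever the treatment does.

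DCR is a named secondary efficacy endpoint. SAP section 7.2.4.3 gives it subgroup analyses and a logistic regression, which inherit the same classification. The trial has one arm, so nothing offsets the bias, and readers may set the result beside the DCR figures in Protocol section 4.1.4.2 (43.8%, 44% and 72%).

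**Working it through.** The plan states no expected DCR and no minimum duration for SD, so there is no figure to reproduce. The check applies the written rules to two subjects and then sizes the effect.

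**Earliest on-schedule scan.** 56 − 7 = 49 days after Day 1 of Course 1. Only a discontinuation scan or another off-schedule scan can give SD before that.

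**Two subjects, each with a readable scan, no meaningful change in the sum of diameters and no new lesion:**

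| Step | Toxicity stop at week 2, scan at week 3 | Clinical progression at week 4, scan at week 6 |
|---|---|---|
| Scan day, against day 49 | 3 × 7 = 21, earlier | 6 × 7 = 42, earlier |
| Target lesions (Appendix A, item 5) | SD | SD |
| Overall response (Table A.1) | SD | SD |
| Item 9 default | NE, not triggered: imaging gave a result | PD, not triggered: imaging gave a result |
| Best overall response | SD | SD, which ranks above PD |
| DCR | counted | counted |
| PFS | no event, follow-up continues | event at week 4 |

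No rule in the plan leads to another score in the toxicity case. In the clinical-progression case a competing rule exists, but it is written only for PFS and the PFS rate.

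**Direction.** The denominator is the full analysis set in any case. The gap can only move a subject from PD or NE into SD, so DCR can only rise.

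**Size.** Shift in DCR = k / N, where k is the number of such subjects and N = 52 is the target in Protocol section 6.2.2.2:

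- k = 0: no shift
- k = 1: 1/52 = 1.9 points
- k = 3: 3/52 = 5.8 points
- k = 5: 5/52 = 9.6 points

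With N = 47, the number required before the dropout allowance, one subject is 1/47 = 2.1 points. The documents give no rate of early stopping with an unchanged scan, so the range of k is an assumption.

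**Illustration.** Take an assumed true count of 23/52 = 44.2% (exact 95% CI 30.5 to 58.7), close to the TAS-102 figures that the protocol cites. Five such subjects make it 28/52 = 53.8% (39.5 to 67.8). The SAP names no interval method for DCR; Clopper-Pearson is used here.

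**The case against.** **The number of cases may be very small.** If one drug is stopped, the other continues (section 8.1). Suspension and dose reduction come before a full stop (section 8.5). The delay criterion in section 8.7 is reached only at 58 days from the start of the last course. Entry requires ECOG 0–1 and a life expectancy of 3 months. Tables 9.a and 9.b mark the discontinuation scan as to be done when necessary, although section 9.2.10 says it should be done. This stands. A reader might infer that DCR is overstated by 6 to 10 points, but the documents do not support any particular number, and the range starts at zero.

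**A discontinuation scan may lie outside the courses.** A course is 28 days of treatment, and a scan up to 28 days after the decision can fall after the last one. This is partly right, and the wording is ambiguous. But the study calendars place discontinuation within the protocol treatment period, DCR refers to response after enrolment, and the week-3 scan lies inside Course 1 on any reading.

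**An imaging-based DCR may differ from a PFS that adds clinical progression.** This also stands. A reader might infer a flat contradiction between DCR and the trial's progression definition. The definitions are different, and the result is an inconsistency that the plan should resolve openly. Nor is a toxicity stop without progression an efficacy failure; the issue there is that an early scan says too little to establish disease control.

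**Responses after PD.** A reader might infer that RR and duration of response are also materially distorted, since a PR dated after PD would be eligible and its duration could end before it began. The wording does not exclude this, but the route is close to hypothetical. Section 8.7 stops treatment at evident PD. The one exception is illustrated by a tumour that has become very small, so that PD is measured from a low nadir, and such a subject would normally have responded already. If PD appears at the first scan, the only reference is baseline, so it means growth.

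**DCR is descriptive.** It has no threshold or comparator. That limits the consequence but does not make the classification right.

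**Conclusion.** The point holds as a defect in the definition of best overall response, with its practical effect on DCR and on DCR's subgroup and logistic analyses. Following the rule as written counts some early stoppers as disease control, always in the favourable direction, at 1.9 points per subject with N = 52. The total of 0 to 9.6 points rests on an assumed 0 to 5 subjects; the defect itself does not depend on that number. The conclusion also assumes that discontinuation scans are eligible, which is the plainer reading but not an explicit one.

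The primary endpoint, PFS, OS and TTF do not use best overall response and are unaffected. RR and duration of response are touched only through the rare post-PD case. This should be corrected before DCR is finalised, but it does not threaten the trial's main conclusion.

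**What to change.** Add to SAP section 7.2.4.2, items 3 and 5, and to Appendix A, item 9:

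- Best overall response is derived only from assessments up to and including the first progression. State that progression here means RECIST or clinical progression, as for PFS.
- SD counts only if documented on a scan, which may be the discontinuation scan, at least 49 days after Day 1 of Course 1 (the lower edge of the Table 9.c window) with no earlier progression.
- A subject without CR, PR or a qualifying SD is scored PD if progression came first and NE if not.

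The 49-day limit is a choice based on the trial's own imaging window; the plan has no SD rule of its own to copy. If the sponsor prefers a purely radiological DCR, the SAP should say so, and the minimum time for SD is still needed.

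The cost is a few sentences. No new data are needed: section 9.2.10 has scan dates entered in the CRF, and the listings in SAP sections 7.2.7.11 and 7.2.7.12 already include treatment start, overall response and the dates of clinical and radiological PD. No treatment rule changes. DCR may come out slightly less favourable.

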OS is the period from the day of enrollment until death by all causes. For surviving subjects, the period is terminated on the final day of confirming survival or data cut-off date, whichever occurs earlier.

[Analysis method]

The analysis will be performed in the same manner as for PFS in the “full analysis set”.

- Response rate (RR)

RR is the percentage of subjects whose best overall response after enrollment according to RECIST ver 1.1 (see Appendix A) is either CR or PR. Overall response will be graded by favorability in the order of CR, PR, SD, PD, and NE.

[Analysis method]

RR and its 95% confidence interval (two-sided) will be calculated in the “full analysis set”.

- Duration of response (DOR)

DOR is the period from the day when either CR or PR is first confirmed until the day of documented PD or the day of death due to all causes, whichever occurs earlier. For surviving subjects without documented PD, the period will be cut off on the final day when specified diagnostic imaging reveals no PD (final day of confirming progression-free survival). For surviving subjects without documented PD for whom curative resection is indicated during protocol treatment, the period will be cut off on the final day when specified preoperative diagnostic imaging reveals no PD (final day of confirming progression-free survival).

[Analysis method] Show the Kaplan-Meier survival curve until the onset of event for the subjects who showed response among the “full analysis set” and calculate the point estimation value of survival rate and its 95% confidence interval (two-sided) at the quantile of survival period and specified time points.

- Disease control rate (DCR)

DCR is the percentage of subjects whose best overall response after enrollment according to RECIST ver 1.1 (see Appendix A) is CR, PR, or SD. Overall response will be graded by favorability in the order of CR, PR, SD, PD, and NE.

CONFIDENTIAL

[Analysis method]

DCR and its 95% confidence interval (two-sided) will be calculated in the “full analysis set”.

- Time to treatment failure (TTF)

TTF is the period from the day of enrollment until the day of the decision to discontinue protocol treatment, the day of documented progression during protocol treatment, or the day of death due to all causes whichever comes earlier.

[Analysis method]

The analysis of TTF will be performed in the same manner as for PFS in the “full analysis set”.

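### RR is defined on best overall response, but the analysis line calculates it on target lesions, which gives a rate that can equal or exceed the defined RR but never fall below it

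*SAP*

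**What the plan says.** SAP version 4.0, section 7.2.4.2, item 3), gives the definition first: "RR is the percentage of subjects whose best overall response after enrollment according to RECIST ver. 1.1 is either complete response or partial response". The analysis method in the same item then reads: "RR of target lesion and its 95% confidence interval (two-sided) will be calculated in the" full analysis set. The current protocol, section 13.3.3.2, has the same definition followed by the same analysis line.

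Protocol Appendix A treats target-lesion response as one of three components of overall response: "Overall Response will be determined with combination of target lesion response, non-target lesion response, appearance of new lesion". The target-lesion PR criterion looks only at the sum of diameters (SoD): "At least a 30% decrease in the SoD of target lesions, taking as reference the baseline SoD". Best overall response is then taken from the overall results, not the target results: "The most favorable overall response through the entire course will be the best overall response".

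For comparison, the DCR analysis line in the same SAP section carries no such qualifier: "DCR and its 95% confidence interval (two-sided) will be calculated in the" full analysis set. The earlier protocol text in the same file has none for RR either: "RR and its 95% confidence interval (two-sided) will be calculated in the" full analysis set. SAP version 1.0 is also without it. The qualifier appears in the SAP from version 2.0 onward. The superseded texts are cited only to show that the words were added.

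**The concern.** The definition and the analysis line sit in one numbered item and name two response variables. A subject whose target lesions shrink by 30% on the same scan that shows a new lesion is a non-responder under the definition and a responder under the analysis line. The protocol and SAP carry the same mismatch, so checking one against the other does not resolve it. An analyst could follow either sentence and claim to have followed the plan.

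At stake is the figure reported for a listed secondary efficacy endpoint. DCR is defined on best overall response, so the subject just described could be counted in RR and not in DCR. SAP 7.2.4.3, item 1), lists RR among the subgroup analyses and refers back to the methods of 7.2.4.1 and 7.2.4.2, so the ambiguity passes into each background factor. No hypothesis test or sample size depends on RR.

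**Working it through.** The documents give no expected RR and no sample size for RR, so there is no stated figure to reproduce. The check is whether the two readings can differ, in which direction, and by how much per subject.

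**Inputs.** The RR definition and analysis line are in SAP 7.2.4.2 item 3) and protocol 13.3.3.2. The rules for overall response are in protocol Appendix A, Table A.1. This table is the relevant one because inclusion criterion 5 requires a measurable lesion and the full analysis set requires that all enrollment criteria be met. The planned N of 52 is from protocol 6.2.2.2 and is used only for scale.

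**Step 1: one scan.** Take five target states (CR, PR, SD, PD, not evaluable), four non-target states (CR, non-CR/non-PD, PD, not evaluable), and new lesion absent or present: 5 × 4 × 2 = 40 combinations.

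- Target CR or PR but not overall CR or PR: 2 target states × (4 non-target states with a new lesion + 1 state, non-target PD, without one) = 2 × 5 = 10. All ten are overall PD.
- Overall CR or PR without target CR or PR: 0. Every row of Table A.1 that gives overall CR or PR requires target CR or PR.

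One combination (target and non-target both not evaluable, no new lesion) is not listed in Table A.1. It was taken as not evaluable and affects neither count. The 10 of 40 is a count of possibilities, not a frequency.

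**Step 2: one subject over all scans.** Any scan with overall CR or PR also shows target CR or PR. Every responder under the definition is therefore also a responder under the analysis line. Let d be the number of subjects with at least one target CR or PR but never an overall CR or PR. Then

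target-lesion RR = defined RR + d/N, with d ≥ 0.

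**Step 3: size.** At N = 52, each discordant subject adds 1/52 = 1.9 points. At the 47 subjects that the protocol requires before allowance for losses, it is 1/47 = 2.1 points. The shift does not depend on the underlying RR. At N = 52:

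- d = 0: no difference
- d = 1: 1.9 points
- d = 2: 2/52 = 3.8 points
- d = 3: 3/52 = 5.8 points

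To set this against sampling error, assume 7, 12 or 18 overall responders out of 52. None of these counts is a planning value in the documents. Exact 95% intervals are used because the SAP names no interval method for RR.

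| Assumed overall responders | d = 0 | d = 1 | d = 3 |
|---|---|---|---|
| 7 | 13.5% (5.6 to 25.8) | 15.4% (6.9 to 28.1) | 19.2% (9.6 to 32.5) |
| 12 | 23.1% (12.5 to 36.8) | 25.0% (14.0 to 38.9) | 28.8% (17.1 to 43.1) |
| 18 | 34.6% (22.0 to 49.1) | 36.5% (23.6 to 51.0) | 40.4% (27.0 to 54.9) |

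**The case against.** The strongest reply is that this is loose wording. RR is a defined term, its definition stands directly above the analysis line, and the SAP version that added the qualifier also added a sentence restating best overall response. The listing in SAP 7.2.7.11 holds the overall result for every subject, so the defined endpoint can be computed. That reading is possible, but nothing in either document confirms it. As written, the line names a different variable.

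The second reply is that few subjects would differ. Someone with an overall PR at one scan and a new lesion later is a responder either way. Protocol 8.7 ends treatment at evident PD. Appendix A calls non-target disease PD alongside a target PR only if the increase outweighs the target shrinkage. All of this stands, and it limits d. It does not make d zero by rule: target shrinkage and a new lesion can appear together at the first 8-week scan. The progression definition in SAP 7.2.4.1 also allows treatment to continue after PD by response criteria in one situation.

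A reader might go further than the documents allow in four ways.

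- That target CR with residual non-target disease, which is overall PR, is also misclassified. It does not change RR, which counts CR and PR together.
- That DOR is bound to conflict with RR. DOR runs from the first CR or PR, and its text does not say whether that response is overall or target.
- That RR would cease to be comparable with the response rates quoted in the protocol's background and rationale. The documents do not state which criteria those rates used.
- That a particular number of subjects would be misclassified. No expected RR and no count of discordant subjects is given.

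**Conclusion.** The definition and the analysis line for RR contradict each other in both current documents. Under the trial's own Appendix A, the target-lesion rate is never below the defined RR and exceeds it by 1.9 points per discordant subject at N = 52. This rests on Table A.1 as printed and on the planned N; the actual full analysis set may be smaller. A reader might infer that RR is overstated. The documents support only that it can be overstated and cannot be understated, because the number of discordant subjects is unknown and may be zero.

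The consequence is confined to a secondary, descriptive endpoint, its subgroup analyses, and possible inconsistency with DCR. The primary test and the sample size are untouched. It is worth correcting because the instruction, followed literally, can produce a figure that is not the endpoint it is labelled as.

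**What to change.** In SAP 7.2.4.2 item 3) and in protocol 13.3.3.2, delete *of target lesion*, so that the line calls for RR (best overall response CR or PR) and its two-sided 95% confidence interval in the full analysis set. If a target-lesion response rate is wanted, list it separately as a supportive figure and label it as such.

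The cost is a wording change in two places. Little target-lesion information is lost, because the waterfall plot, the spider plot and the RECIST listing already show it. The one downside for the sponsor is that RR may come out slightly less favourable than the target-lesion rate.
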